5.5 Vital signs and ECG – definition of clinically notable values

The following two tables show the clinical notable criteria for vital signs and QTcF respectively.

Table 5.5-1 Clinical notable criteria for vital signs

Vital sign parameter (unit)	Lower bound of clinically notable range	Upper bound of clinically notable range
Notable value considering newly occurring or worsening cases		
Systolic blood pressure (mmHg)	< 75	> 200
Diastolic blood pressure (mmHg)	< 40	> 115
Pulse rate (bpm)	< 40	> 130
Notable change from baseline		
Systolic blood pressure (mmHg)	≤ 90 and decrease from baseline by ≥ 20	≥ 180 and increase from baseline by ≥ 20
Diastolic blood pressure (mmHg)	≤ 50 and decrease from baseline by ≥ 15	≥ 105 and increase from baseline by ≥ 15
Pulse rate (bpm)	≤ 50 and decrease from baseline by ≥ 15	≥ 120 and increase from baseline by ≥ 15
Weight (kg)	Decrease > 7% from baseline	Increase > 7% from baseline

Table 5.5-2 Clinical notable criteria for QTcF (Fridericia's formula)

ECG parameter (unit)	Clinically notable range
Notable value considering newly occurring or worsening cases	
QTc (msec)	> 450
QTc (msec)	> 480
QTc (msec)	> 500
Notable change from baseline	
QTc (msec)	30 – 60
QTc (msec)	> 60
Combined criterion	
QTc (msec)	> 500 & increase > 60

5.6 Details on derivation of variables

5.6.1 Derivation of baseline disease characteristics

- Airflow limitation is classified based on % of predicted FEV₁ and FEV₁/FVC post bronchodilation ([GOLD 2018](#)):
 - Mild (GOLD 1): FEV₁/FVC < 70 % and % of predicted FEV₁ ≥ 80 %
 - Moderate (GOLD 2): FEV₁/FVC < 70 % and 50% ≤ % of predicted FEV₁ < 80 %
 - Severe (GOLD 3): FEV₁/FVC < 70 % and 30% ≤ % of predicted FEV₁ < 50 %
 - Very Severe (GOLD 4): FEV₁/FVC < 70 % and % of predicted FEV₁ < 30 %

- Patients will be classified based on a combined assessment of COPD using the number of COPD exacerbations and COPD exacerbations leading to hospital admission in the last year, and CAT at Run-In 1 visit.
The following algorithm will be applied based on the standard in [GOLD 2018](#):
 - Group A:
history of exacerbation ≤ 1 not leading to hospital admission and CAT < 10
 - Group B:
history of exacerbation ≤ 1 not leading to hospital admission and CAT ≥ 10
 - Group C:
(history of exacerbation ≥ 2 or ≥ 1 leading to hospital admission) and CAT < 10
 - Group D:
(history of exacerbation ≥ 2 or ≥ 1 leading to hospital admission) and CAT ≥ 10
- Duration of COPD is calculated from the date of COPD first diagnosed as recorded on the eCRF until the date of Visit 1. If the date is missing in day and month, the missing date part was imputed as 01-July if the year is before Visit 1 and as 01-January if the year is the same as the year of Visit 1. If the date is missing in day only, the missing day was imputed as 15 if month/year is before Visit 1 and as 01 if month/year is the same as of Visit 1.
- Cardiovascular risk factors at baseline: Seven cardiovascular risk factors are defined.
 1. CCV history/condition = at least one out of: Myocardial infarction, Stroke, Peripheral arterial disease, Coronary artery bypass graft, or Percutaneous transluminal coronary angioplasty, as reported on the eCRF page of "Medical History – Protocol solicited events – Cardiovascular events".
 2. Hypertension, as reported on the eCRF page of "Medical History – Protocol solicited events – Cardiovascular events".
 3. Hyperlipidemia = at least one out of: Hyperlipidemia, Hypercholesterolemia, as reported on the eCRF page of "Medical History – Protocol solicited events – Cardiovascular events".
 4. Diabetes mellitus = Type 1 or Type 2 diabetes mellitus, as reported on the eCRF page of "Medical History – Protocol solicited events – Cardiovascular events".
 5. Obesity at baseline (i.e., BMI > 30 kg/m²).
 6. Age ≥ 65 years.
 7. Current smoker at screening.

5.6.2 E-RS total and subscale scores

The E-RS total symptom score will be derived as the sum of items 1 to 11 (items 12 – 14 will not be used for the E-RS), the RS-Breathlessness score as the sum of items 7 - 11, the RS-Cough & Sputum scores as the sum of items 2 - 4 and the RS-Chest Symptoms score as the sum of items 1, 5, 6.

The mean baseline E-RS Total and subscale scores will be the average of the corresponding daily scores from the run-in period (which is usually a 14 day period), the last 14 days from Run-In 1 visit up to a day before the first dose of double-blind treatment will be included. A patient needs to have at least 8 days of data from the run-in period in order for the mean baseline

score to be calculated. If there are less than 8 days of data available during the last 14 days from the run-in period, then use the last 7 days of data if there are at least 4 days of data available to calculate the mean.

For the derivation on-treatment mean weekly and mean monthly scores, only values from Day 1 up to the date of last dose of double-blind treatment will be considered. Missing diary data will not be imputed.

The daily scores will be averaged for each week (Week 1, Week 2, etc.). A patient needs to have at least 4 days of data in any week in order for the mean score to be calculated.

Monthly means over a 4-week period will also be calculated. A patient needs to have at least 3 weekly means in that month in order for the monthly mean score to be calculated.

5.6.3 CASA-Q domain scores

The CASA-Q is a validated questionnaire instrument used to measure cough and sputum production, and their impact in patients with chronic obstructive pulmonary disease (COPD) and/or chronic bronchitis ([Crawford et al 2008](#)). It contains a total of 20 items on a 5-step scale distributed in 4 domains: Cough symptoms (3 items, question 1-3), Cough impact (8 items, question 4-11), Sputum symptoms (3 items, question 12-14) and Sputum impact (6 items, question 15-20).

Each item is answered on a scale from 'never' to 'always' (for frequency) or from 'not at all' to 'a lot/extremely' (for intensity), each type using five categories (1-5) as applicable. All items are rescored from 1-5 to 0-4 and then reverse scored such that better responses have higher scores.

There are only domain scores and no overall score. The four domains are Cough symptoms, cough impact, sputum symptoms and sputum impact with a range of 0-100. Higher scores associated with fewer symptoms/less impact due to cough or sputum.

Within each domain, items are summed and rescaled using the following algorithm:

CASA-Q domain scores= (sum of rescored items) / (range of rescored items) ×100

A domain score will only be derived if data of all corresponding items are available.

Baseline CASA-Q domain score is defined as the last CASA-Q measurement before first dose of double-blind treatment.

5.6.4 SGRQ total and component scores

The algorithm below is based on [SGRQ Manual Version 2.3, June 2009](#).

The St. George Respiratory Questionnaire (SGRQ) contains 50 items divided into three components: "Symptoms" concerned with respiratory symptoms, their frequency and severity; "Activity" concerned with activities that cause or are limited by breathlessness; and "Impacts" which covers a range of aspects concerned with social functioning and psychological disturbances resulting from airway disease. A score will be calculated for each component and a "Total" score will also be calculated. In each case the lowest possible value is zero and the highest 100. Higher values correspond to greater impairment of quality of life.

SGRQ scoring algorithm

Principle of calculation

Each response will be given a unique empirically derived weight between 0 and 100, the weights of all responses will be summed up and divided by the maximum possible score and expressed as a percentage.

Each component of the questionnaire is scored separately in three steps:

1. The weights for all items with positive responses are summed.
2. The weights for missed items are deducted from the maximum possible weight for each component. The weights for all missed items are deducted from the maximum possible weight for the Total score.
3. The score is calculated by dividing the summed weights by the adjusted maximum possible weight for that component and expressing the result as a percentage. The Total score is calculated in similar way.

Sum of maximum possible weights for each component and Total:

Symptoms	662.5
Activity	1209.1
Impacts	2117.8
Total	3989.4

(Note: these are the maximum possible weights that could be obtained for the worst possible state of the patient).

Symptoms component is calculated from the summed weights for the positive responses to questions 1-8 (Part 1).

Activity component is calculated from the summed weights for the positive responses to questions 11 – 17 (Part 2, Section 2) and 36 – 44 (Part 2, Section 6) on the questionnaire.

Impacts component is calculated from the summed weights for the positive responses to questions 9-10 (Part 2, Section 1), 18 – 35 (Part 2, Sections 3 - 5), and 45 – 50 (Part 2, Section 7) on the questionnaire.

Total score is calculated by summing all positive responses in the questionnaire and expressing the result as a percentage of the total weight for the questionnaire.

Handling of missing items

Symptoms: The Symptoms component tolerates a maximum of 2 missed items. The weight for the missed item is subtracted from the total possible weight for the Symptoms component (662.5) and from the Total weight (3989.4).

Activity: The Activity component tolerates a maximum of 4 missed items. The weight for the missed item is subtracted from the total possible weight for the Activity component (1209.1) and from the Total weight (3989.4).

[REDACTED]

[REDACTED]

[REDACTED]

[REDACTED]

[REDACTED]

[REDACTED]

[REDACTED]

[REDACTED]

[REDACTED]

[REDACTED]

[REDACTED]

[REDACTED]

[REDACTED]

[REDACTED]

[figure not shown]
5.6.10 Pharmacokinetic parameter

The exposure threshold of $C_{min,ss}=2942$ ng/mL is defined based on the exposure threshold $AUC_{0-24h,ss}= 91700$ ng×h/mL using the following formula:

$$\log(C_{min,ss}) = (\log(AUC_{0-24h,ss}/100) - 1.47)/0.67$$

The logarithm to the natural base is used.

The regression line was determined from subjects who received either 450 mg BID or 750 mg BID and for which $AUC_{0-24h,ss}$ could be estimated as two times $AUC_{0-12h,ss}$. The data included PK from 8 subjects from study CQBW251B1101, 23 subjects from CQBW251X2101 and 39 subjects from study CQBW251X2102. For the CF patients in study CQBW251X2101, which had PK assessments up to 8h, $AUC_{0-12h,ss}$ was determined by imputing the steady state trough concentration at 12h to be equal to the steady state trough concentration at 0h.

AUC0-8h will be derived using a trapezoidal rule. If the 0h or the 8h concentration is missing the AUC0-8h will be set to missing. AUC0-12hr will be based on the observed concentrations from 0 to 8hr and extrapolation up to 12h (using trapezoidal rule). The daily drug exposure AUC0-24hr will then be estimated as 2 x AUC0-12hr.

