Clinical monitoring includes the use of an electronic diary with the EXACT questionnaire to enable daily symptoms assessment, as well as safety assessments during visit days at the investigational site. These include a careful assessment of adverse events, as well as triplicate ECGs, hematologic and clinical chemistry laboratory assessments, urinalysis and vital signs measurements. As a formal thorough QT assessment of QBW251 has not been completed, triplicate ECGs pre- and post-dose (at the time to reach maximum (peak) plasma concentration following drug administration (T_{max})) will be performed at Day 1, at Day 15 (when all patients have reached steady state concentration of the investigational drug), and at Day 169 (end of treatment). These assessments will be complemented by the corresponding PK sampling (trough and C_{max}). The PK sampling is also part of a more granular PK monitoring (detailed in schedule of assessment [Table 8-1](#)), which has been put in place to ensure that patient exposures are in general consistent with a threshold (area under the plasma concentration curve over 24 hours (AUC_{0-24h}) = 91 700 ng×h/mL) that was established based on animal (monkey) data. As this threshold represents an average of the exposures observed in those animals after 39 weeks of treatment with QBW251, this limit is not absolute and few patients are expected to exceed it. In prior QBW251 studies, patients with exposures above this threshold reported either no adverse events or mild to moderate ones.

In addition to the sampling described above, the PK monitoring plan will generate C_{min} data at all visits and additional PK samples are requested to be taken in case of treatment-emergent serious adverse events. Study drug discontinuation and cohort stopping rules related to exposure have been introduced into the protocol as well (see [Section 9.1.4.1](#))

Finally a sub-group of approximately 48 patients will undergo serial PK assessments to further characterize the PK profile of QBW251 before transitioning into the confirmatory Phase 3.

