Table 8-3 Timed assessments for Day 1 and Day 15 for subjects participating in the additional PK sampling sub-group (additional PK timepoints)

	Time Point ¹	PROs at site	Urine Sample	ECG	Vital Signs ³	Hemato-logy/ Blood Chemis-try	Spiro-metry ⁴	PK Blood Samp-ling
Day 1	Prior to -45 min	X						
			X	X ²	X			
	Prior to -45 min	Randomization						
	-45 min						X	
	-45 to -20 min approximately					X		X
	-15 min						X	
	0	Study drug administered in clinic						
	1 h							X
	2 h							X
	4 h				X ²			X
6 h							X	
8 h							X	
Week 2	Prior to Study drug			X ²	X			

	Time Point ¹	PROs at site	Urine Sample	ECG	Vital Signs ³	Hemato-logy/ Blood Chemis-try	Spiro-metry ⁴	PK Blood Samp-ling
	Prior to Study drug							X
	0	Study drug administered in clinic						
	1 h							X
	2 h							X
	4 h			X ²				X
	6 h							X
	8 h							X

¹ Time relates to the dose given from spirometry device at visit unless otherwise specified

² Triplicate ECG measurements required.

³ Systolic/diastolic blood pressure and heart rate

⁴ A minimum 3 minutes rest period from the beginning of ECG assessments to the start of spirometry maneuvers must be observed at all times

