2.1.1.1 Study day

Study day will be defined as the number of days since the date of first dose of double-blind treatment. The date of first dose of double-blind treatment will be defined as Day 1 and the day before the first dose of study drug will be defined as Day -1.

Therefore, for a particular date, study day will be calculated as follows:

for dates on or after the first date of double-blind treatment,

$$\text{Study day} = \text{Assessment date} - \text{Date of first dose of double-blind treatment} + 1;$$

for dates prior to the first date of double-blind treatment,

Study day = Assessment date – Date of first dose of double-blind treatment.

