2.9 Pharmacokinetic endpoints

PK measurements will be analyzed as reported; no visit windowing will be applied.

Descriptive summary statistics of QBW251B plasma concentration data will be provided by treatment and visit/sampling time point, including the frequency (n, %) of concentrations below the lower limit of quantification (LLOQ). Summary statistics will include mean (arithmetic and geometric), standard deviation, coefficient of variation (arithmetic and geometric), median, minimum and maximum. An exception to this is T_{max} where median, minimum and maximum will be presented. Concentrations below LLOQ will be treated as zero in summary statistics and for PK parameter calculations.

Pharmacokinetic parameters will be determined using non-compartmental method(s).

Summary of PK parameter of all patients in the PK set will include trough concentration C_{min} on all visits and C_{max} on Day 1, Week 2 and Week 24. Summary of PK parameter for patients in the PK serial sub-group will include C_{min} , C_{max} , AUC_{0-8h} , AUC_{0-24h} , and T_{max} on Day 1 and Week 2.

The number and percentage of patients in the PK serial sub-group above the exposure threshold of $AUC_{0-24h,ss} = 91700 \text{ ng}\times\text{h/mL}$ will be presented overall and by visit.

The number and percentage of patients in the PK set above the exposure threshold $C_{min,ss} = 2942 \text{ ng/mL}$ will be presented overall and by visit. This threshold is defined based on the exposure threshold $AUC_{0-24h,ss} = 91700 \text{ ng}\times\text{h/mL}$.

Details on derivation of exposure threshold and AUC_{0-8h} , AUC_{0-24h} are provided in [Section 5.6](#).

In addition, the plasma concentration data from this study may be combined with data from other studies to perform a population PK analysis, which will follow the principles outlined in the [FDA Guidance for Industry 1999](#). These results, if performed, will be reported outside of the CSR.

█ █

█

█ █

█

[REDACTED]

[REDACTED]

[REDACTED]

[REDACTED]

[REDACTED]

[REDACTED]

[REDACTED]

[REDACTED]

[REDACTED]

[REDACTED]

[REDACTED]

[REDACTED]

[REDACTED]

[REDACTED]

[REDACTED]

[REDACTED]

[REDACTED]

[REDACTED]

[REDACTED]

[REDACTED]

[REDACTED]

[REDACTED]

[REDACTED]

[REDACTED]

[REDACTED]

[REDACTED]

[REDACTED]

[REDACTED]

[REDACTED]

[REDACTED]

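### SAP 5.6.10 discards a Day 1 AUC when the pre-dose sample is lost, although that concentration is known to be zero; it also has no rule for lost 1 to 6 h samples

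*SAP*

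**What the plan says.** Protocol Table 8-3 schedules serial PK samples pre-dose and at 1, 2, 4, 6 and 8 h on Day 1 and Day 15 (Week 2). Protocol 4.5 gives the size of the group: "Finally a sub-group of approximately 48 patients will undergo serial PK assessments".

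SAP 5.6.10 sets out the calculation. "AUC0-8h will be derived using a trapezoidal rule", and "If the 0h or the 8h concentration is missing the AUC0-8h will be set to missing". AUC0-12h takes the observed 0 to 8 h concentrations and extends them to 12 h by trapezoid. Then "The daily drug exposure AUC0-24hr will then be estimated as 2 x AUC0-12hr".

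SAP 2.9 adds: "Concentrations below LLOQ will be treated as zero in summary statistics and for PK parameter calculations". Protocol 8.5.1 has results below LLOQ reported as zero but missing samples labelled as missing.

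SAP 2.1.1.1 fixes the start of dosing: "The date of first dose of double-blind treatment will be defined as Day 1". SAP 2.2 admits a consenting patient to the serial sub-group with a single evaluable concentration. SAP 2.9 summarises AUC0-8h and AUC0-24h on Day 1 and Week 2, and counts sub-group patients above a steady-state AUC0-24h of 91700 ng×h/mL.

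**The concern.** The rule treats the 0 h sample alike at the two visits, but the samples are not alike. At Week 2 the 0 h concentration is a trough that differs between patients and cannot be known without the sample, so voiding is reasonable. On Day 1 no study drug has yet been given, so a lost sample takes no information with it.

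The rule also looks only at the two ends of the profile. Read literally, a profile holding only 0 h and 8 h yields an AUC, while a Day 1 profile complete except for its pre-dose sample yields none.

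AUC on Days 1 and 15 in this sub-group is a listed secondary endpoint, and the sub-group is small. Needless deletion costs precision, and a profile that has lost its peak samples will usually give too low an AUC.

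**Working it through.** **The plan's own figure.** SAP 5.6.10 derives a Cmin,ss threshold from 91700: exp((ln(91700/100) − 1.47)/0.67) = 2941.65, which rounds to the stated 2942 ng/mL. It reproduces and is not in question.

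**Part 1: lost Day 1 pre-dose sample**

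1. The Day 1 0 h sample precedes the first dose (Table 8-3, SAP 2.1.1.1). The half-life is 10-16 h (Protocol 4.2), and screening to Day 1 takes about 21 days, or 21 × 24/16 = 31.5 half-lives at the longer value. The true concentration is zero.
2. If the sample is collected and assayed, a result below LLOQ enters as zero, and the first trapezoid is 0.5 × (0 + C1) × 1 h.
3. If the sample is lost, it is labelled missing. The LLOQ rule does not reach it, and AUC0-8h is voided. SAP 5.6.10 does not say separately that AUC0-12h and AUC0-24h are voided, but both are built on the 0 to 8 h concentrations.
4. Entering zero gives the same first trapezoid as step 2, so the AUC equals that of the complete profile (0% error).

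If the 48 patients follow the randomization ratio (an assumption), a 25, 75 or 150 mg arm holds 48 × 1/9 = 5.3 to 48 × 1/7 = 6.9 patients, so one deleted profile is about 15-19% of that arm. The 300 mg arm holds 48 × 2/9 = 10.7 to 48 × 2/7 = 13.7, so one profile is about 7-9%.

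**Part 2: lost 1 to 6 h samples, Week 2 AUC0-24h**

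Inputs: half-life 10 and 16 h (Protocol 4.2). Assumed: one-compartment model, absorption rate ka 0.4 and 0.8 per h, linear trapezoid, 12 h concentration equal to the 0 h trough. With ke = ln 2/half-life, the steady-state concentration on 12-hourly dosing is proportional to e^(−ke·t)/(1 − e^(−12ke)) − e^(−ka·t)/(1 − e^(−12ka)).

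Worked case (half-life 10 h, ka 0.8). Concentrations at 0, 1, 2, 4, 6, 8 h are 0.771, 1.203, 1.340, 1.301, 1.160, 1.015.

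- All samples: AUC0-8h = 0.987 + 1.272 + 2.641 + 2.461 + 2.175 = 9.536. The 8 to 12 h piece is 2 × (1.015 + 0.771) = 3.572, so AUC0-12h = 13.108.
- 2 h and 4 h lost: 0.987 + 2.5 × (1.203 + 1.160) + 2.175 + 3.572 = 12.642, or −3.6%.
- 1, 2 and 4 h lost: 3 × (0.771 + 1.160) + 2.175 + 3.572 = 11.540, or −12.0%.
- All four lost: 4 × (0.771 + 1.015) + 3.572 = 10.716, or −18.2%.

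Doubling to AUC0-24h leaves the percentages unchanged. Across the four combinations of half-life and ka:

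| Samples lost | Change in Week 2 AUC0-24h |
|---|---|
| any one | 0 to −1.2% |
| 4, 6 h | −1.1% to −2.5% |
| 2, 4 h | −1.8% to −3.6% |
| 1, 2, 4 h | −4.3% to −12.0% |
| 1, 2, 4, 6 h | −7.5% to −18.2% |

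Fixing the single-dose Tmax at 2 to 4 h instead of fixing ka gives −1.0% to −3.5%, −7.2% to −15.6% and −11.2% to −21.8% for the three losses in the worked case.

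**The case against.** A reader might infer that the rule hides exceedance of the 91700 threshold on a large scale. Day 1 AUC0-8h does fall by 21-34% when 1, 2 and 4 h are lost and by 38-52% when all four are lost, under the same ka range. Those figures do not carry over. The threshold is a steady-state AUC0-24h and Day 1 is a first dose. So although SAP 2.9 tabulates the count by visit, Week 2 is where it has meaning, and there the 8 to 12 h segment dilutes the error. That objection stands.

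It is also fair that large errors need three or four interior samples lost while both 0 h and 8 h were obtained, and that nothing shows this to be expected even once. SAP 2.9 counts exceedance separately by Cmin,ss in the whole PK set, with no trapezoid. Low bias is not universal either: losing 4 h and 6 h with an early peak gave +0.1% to +0.3% in Week 2 AUC0-8h, and losing 1 h with an assumed 0.9 h absorption lag gave +4.5%. At ka 0.4 the model's Day 1 Tmax is 5.3-6.2 h, later than the 3 or 4 h at which the protocol times its post-dose ECG, so the percentages are illustrative.

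Voiding every profile with two consecutive losses is a tempting remedy, but it would delete usable data. At Week 2, losing 4 h and 6 h costs only 1.1-2.5% of AUC0-24h.

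None of this answers the Day 1 pre-dose point. Its frequency is unknown, but when it occurs the deletion serves no purpose.

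**Conclusion.** The Day 1 point holds without any model: the rule deletes an AUC that can be computed exactly. It applies only when the pre-dose sample is missing, not when it reads below LLOQ.

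The gap on interior samples is real but secondary. Its size rests on the assumed one-compartment model: about 1% for one lost sample, and more than about 4% at Week 2 in the worked losses only when three or four are gone. The documents do not support a claim that the rule materially conceals exceedance.

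The effect is confined to descriptive PK summaries in a sub-group of about 48. The primary FEV1 analysis and the Cmin-based count are untouched. No missing-sample rate is given, so the overall effect cannot be computed.

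**What to change.** Amend SAP 5.6.10 in two places.

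1. On Day 1, set a missing pre-dose concentration to zero and calculate AUC0-8h, AUC0-12h and AUC0-24h as usual. Keep voiding on a missing 0 h sample for Week 2 only, and leave the 8 h rule as it is.
2. Flag profiles with lost samples between 1 h and 6 h. Present the AUC summary and the count above 91700 with and without profiles missing three or more of the 1, 2, 4 and 6 h samples.

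The first change is one sentence, with no loss of data or validity. The second costs a flag and a repeated summary in a small sub-group. The cut at three is a judgement, which is why it is used for a comparison and not to exclude profiles. Both are best settled before the concentrations are seen.

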8.5 Additional assessments

8.5.1 Pharmacokinetics

Blood samples will be obtained from all subjects as per visits and timepoints indicated in [Table 8-1](#) and [Table 8-2](#).

In approximately 48 subjects, additional PK samples at Day 1 and Day 15 will be collected, as per [Table 8-3](#), to examine the time-concentration profiles of QBW251 after single dose and multiple doses in the COPD patients. Furthermore, additional PK samples will be collected,

where possible, from patients experiencing a treatment-emergent SAE, unless a scheduled PK sampling occurs within 7 days of the start date of the SAE.

While PK sampling occurs across all treatment arms including placebo, plasma PK samples will be evaluated only in subjects who have been administered QBW251. QBW251 will be analyzed by a validated LC-MS/MS method with an anticipated lower limit of quantification (LLOQ) of 1 ng/mL of QBW251. Concentration below the LLOQ will be reported as zero and missing data will be labeled as such in the bioanalytical report.

[REDACTED]

[REDACTED]

[REDACTED]

[REDACTED]

[REDACTED]

[figure not shown]
[figure not shown]

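### Doubling AUC0-12h to get AUC0-24h is a steady-state shortcut, and the SAP also applies it to Day 1, where at the nominal 12 h interval it gives too low a value

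*SAP*

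**What the plan says.** SAP 5.6.10 builds daily exposure in two steps. First, "AUC0-12hr will be based on the observed concentrations from 0 to 8hr and extrapolation up to 12h (using trapezoidal rule". Then, "The daily drug exposure AUC0-24hr will then be estimated as 2 x AUC0-12hr". Neither step is restricted by visit, and no separate Day 1 rule appears. Earlier in the same section, for the regression that links trough to AUC, the doubling is applied only to quantities marked as steady state.

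SAP 2.9 fixes where the result is used: "Summary of PK parameter for patients in the PK serial sub-group will include" AUC0-24h, alongside Cmin, Cmax, AUC0-8h and Tmax, for both Day 1 and Week 2. It also plans, overall and by visit, "The number and percentage of patients in the PK serial sub-group above the exposure threshold of" 91,700 ng×h/mL, a limit labelled as steady state.

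Protocol 8.5.1 gives the purpose of the serial samples as "to examine the time-concentration profiles of QBW251 after single dose and multiple doses in the COPD patients". Protocol 4.5 places steady state "at Day 15 (when all patients have reached steady state concentration of the investigational drug". AUC on Days 1 and 15 in the sub-group is a secondary endpoint (Protocol section 2).

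**The concern.** Doubling a 12 h area gives a 24 h area only when the two dosing intervals carry the same exposure, which is the steady-state condition. On Day 1 the second interval contains the second dose plus what remains of the first. With a half-life close to the dosing interval, that remainder is substantial.

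At stake is the accuracy of one reported quantity. A Day 1 figure labelled as 24 h exposure would be too low, while the Week 2 figure beside it would not have this fault. A reader comparing daily exposure across the two visits would see too large a rise.

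**Working it through.** **Inputs from the documents.** Single-dose half-life 10 to 16 h (Protocol 4.2). Doses about 12 h apart, with clock windows of roughly 7 to 10 a.m. and 8 to 11 p.m. (Protocol 6.7.2), so opposite window ends give 10 to 16 h. Serial samples at 0, 1, 2, 4, 6 and 8 h (Protocol Table 8-3).

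**Assumptions, not in the documents.** Linear superposition; the shape of the profile; and Tmax 3 h, taken from the 3 h post-dose sample in Table 8-2, or rapid absorption.

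**The section's own figure.** exp[(ln(91700/100) − 1.47)/0.67] = 2941.65, which rounds to the stated 2942 ng/mL. It reproduces. The SAP states no numerical Day 1 AUC.

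**Direction.** Let A(t) be the first-dose area from 0 to t and τ the first interval. The actual Day 1 AUC0-24h is A(24) + A(24 − τ). At τ = 12 h this equals 2A(12) + [A(24) − A(12)]. The SAP value is 2A(12). The omitted term is the first dose's area from 12 to 24 h, which is positive.

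**Size, one compartment, 12 h, exact AUC0-12h.** With rapid absorption and x = 2^(−12/half-life), the understatement is x/(2 + x).

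| Half-life | x | Rapid absorption | Tmax 3 h |
|---|---|---|---|
| 10 h | 0.4353 | 0.4353/2.4353 = 17.9% | 20.0% |
| 13 h | 0.5274 | 0.5274/2.5274 = 20.9% | 22.8% |
| 16 h | 0.5946 | 0.5946/2.5946 = 22.9% | 24.7% |

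**Size, two-phase decline, 12 h, exact AUC0-12h.** Assumed: fast half-life 1.5 or 2.5 h, slow phase 10% or 30% of the initial concentration, terminal half-life 10 or 16 h, rapid absorption. Areas are in relative units.
- Smallest (10 h, 2.5 h, 10%): A(12) = 3.944, A(24) = 4.411; 0.467/(2 × 3.944 + 0.467) = 5.6%.
- Largest (16 h, 1.5 h, 30%): A(12) = 4.316, A(24) = 5.991; 1.675/(2 × 4.316 + 1.675) = 16.3%.
- With absorption at 1 per hour, the range becomes 6.5 to 17.5%.

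**Effect of the first interval (exact AUC0-12h).** One compartment, rapid absorption or Tmax 3 h: 21.1 to 28.3% at 10 h, 16.0 to 22.6% at 13 h, 13.8 to 20.3% at 14 h, 8.6 to 14.9% at 16 h. Two-phase with absorption: 3.9 to 14.1% at 14 h; at 16 h, from a 0.1% overstatement to a 9.7% understatement.

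**Effect of the C12 rule (12 h, planned sampling times, linear trapezoids).** The SAP does not say how C12 is obtained.
- Log-linear from 6 and 8 h: 21.0 to 25.7% low (one compartment, Tmax 3 h); 8.2 to 20.0% (two-phase with absorption).
- C8 carried forward: 17.9 to 23.7% and 2.7 to 16.3%. At a 16 h interval this rule overstates by up to 4.2% in the most extreme two-phase case.

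**The case against.** The strongest reply is that little turns on this. The endpoint is AUC on Days 1 and 15, not AUC0-24h specifically. AUC0-8h on Day 1 is already planned and is sound. The formula is disclosed and described as an estimate, so halving the value recovers AUC0-12h. The SAP plans no accumulation ratio, and the ratio of two doubled values would in any case be the AUC0-12h ratio. All of this stands and keeps the point minor. It does not make the Day 1 quantity an AUC0-24h.

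The second reply concerns certainty. The 18 to 25% rests on mono-exponential decline, for which the documents give only a half-life. The protocol also reports over-proportional exposure at high doses (12.4.2) and time-dependent inhibition and induction of CYP3A4/5 (6.2.1.1), neither of which is modelled. That stands too, so no single size can be claimed. Nor is the bias downward under every conceivable condition. The reversals, however, need long first intervals, and a 16 h daytime gap sits poorly with the instruction of about 12 h. It would leave 8 h overnight, whereas spirometry visits require 10 to 14 h after the evening dose.

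Stronger readings that a reader might infer, and why they fail:
- *C12 would be set to zero on Day 1.* Section 5.6.10 does mention "imputing the steady state trough concentration at 12h to be equal to the steady state trough concentration at 0h", but for an earlier study's steady-state data. For this trial it prescribes extrapolation from the observed 0 to 8 h.
- *The 450 mg arm was stopped on biased values.* The stopping test uses patients with at least 4 weeks of treatment (Protocol 12.7.1), not Day 1 profiles.
- *The threshold counts are wrong.* Serial samples exist only on Day 1 and Week 2, so the by-visit AUC count implies a Day 1 row. That row says little about a steady-state limit, but it is not an error. For the trough count ("The number and percentage of patients in the PK set above the exposure threshold"), the SAP does not say that Day 1 is included.

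**Conclusion.** The point holds and is minor. As written, the SAP produces a Day 1 AUC0-24h that is biased low at the nominal 12 h interval. That direction needs only superposition and the fact that some first dose remains after 12 h, so confidence in it is high. Confidence in the size is not: about 18 to 25% under one-compartment kinetics and about 6 to 16% in the assumed two-phase profile, both with an exact AUC0-12h. Longer first intervals reduce it, and extreme ones could remove or slightly reverse it.

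The consequence is confined to descriptive secondary PK output in about 48 patients. Week 2 AUC, Day 1 AUC0-8h, the arm-stopping test and the primary FEV1 dose-response analysis are not affected.

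**What to change.** In SAP 5.6.10, limit the doubling to Week 2 and state how C12 is extrapolated from the 0 to 8 h samples. In SAP 2.9, drop AUC0-24h from the Day 1 summary. Keep AUC0-8h there and, if a longer window is wanted, add AUC0-12h under that name. Present the count above the AUC0-24h,ss limit of 91,700 ng×h/mL, including its overall figure, from Week 2 only.

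The cost is a wording change in two SAP sections and the loss of one derived Day 1 parameter. No new samples are needed.
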